Conventional restorative treatments do not work for older adults. The dental treatment needs of older adults differ from those of younger adults and thus makes diagnosis and treatment planning more complex due to age related changes to the enamel, dentine, and pulp chamber. For this reason, results of work conducted in children cannot be extrapolated to older adults (**RQ-1**). The majority of tooth decay in older adults is failure of restorations at the gum line and in exposed roots. These lesions are difficult to diagnose or restore, even for experienced dentists. A randomized trial in older adults with root caries treated the decayed tooth surfaces with either ART or conventional treatment (using a dental drill) and found that ART had a similar restoration survival rate (87% vs. 91%). Fluoride varnish and SDF are also both effective in arresting and preventing new tooth lesions.

Silver Diamine Fluoride (SDF) has been long used to arrest caries in other countries and is now widely available in the United States. The liquid agent is painted on the decayed tooth or root and the treated lesion hardens, while the lesion depth decreases and becomes resistant to caries bacteria. SDF inhibits the decay process by restricting the bacterial metabolic and reproductive functions leading to bacterial killing. Thus, silver is an antimicrobial that kills cariogenic bacteria far superior to other antimicrobial medicaments. Annual 38% SDF has been effective in arresting and preventing root caries lesions among older adults in clinical trials. Recently, the American Dental Association evidence-based clinical practice guidelines recommends bi-annual application of SDF on permanent teeth.

Despite the greater dental caries burden, there are no community-based public health interventions that exist for low-income older adults like those for children, and the current clinic-based dental care delivery system is expensive and ill adapted (**RQ-1**). For any caries preventive/treatment intervention to be useful on a population level, 5 presumed attributes are necessary: pain and infection control, simplicity of use, cost affordability, minimal personnel time and training, and non-invasive. Our proposed non-surgical interventions can meet this criteria and provide evidence (**RQ-5**).

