### **Baseline Dental Exam**

- Dentists will administer the Safety Questionnaire (Pre-Exam).
- Hygienists will perform initial dental exam examination at participant's respective housing facility to determine eligibility to continue in the clinical trial based on caries status.
- Study staff will record results of dental exam examination.
- Hygienists, under the direction of the study dentist, will proceed as follows:
- If the participant has an urgent cavity or another serious dental problem, they will be instructed to go for dental care immediately and their participation will end.
- If the participant has no cavities or other urgent problems, they will be instructed to continue regular visits with their dentist and their participation will end.
- If the participant has cavities that require treatment but no urgent problems, they will receive one of two treatments at this visit and will continue to participate in the research. Hygienists will administer the intervention treatment (based on study arm) to all untreated active root or coronal carious lesion with ICDAS-II lesion severity code of 3 or greater.
- If a participant reports any issue with the applied treatment within one week of the treatment date, the study team will return to the housing facility to examine and correct the treated tooth as needed. Within 48 hours, the study team will call the participant to ask the participant if the issue has been resolved and will administer a paper safety questionnaire. The completed paper safety questionnaire will be stored in the CRF folder and documentation of the return visit/treatment will be added to the participant's electronic record.

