### 11.2 Sample Size Considerations (RC-3)

For continuous outcomes we computed power using a variance correction (i.e., variance inflation factor) to take into account possible correlations of outcomes within cluster. All computations of required effective samples sizes (or corresponding power) were done using the PASS 2005 software. For binary outcomes, we used a specialized program for cluster randomization (a non-inferiority test comparing two proportions).

The primary outcome tooth pain was defined as change in pain (based on a 100-mm visual analogue pain scale (VAS), where higher is worse pain) from baseline to 1 year. We assume a mean difference of 0 between SDF and ART+FV, and consider non-inferiority to be within a margin (mean difference) of 8 between SDF and ART+FV arms; and based on prior literature also assume a common standard deviation of 25. Further, we assumed an average of 25 subjects recruited per site, an intraclass correlation (ICC) of 0.01 (based on prior studies and literature), and a 15% dropout rate (based on prior studies). The use of a 0.025 alpha-level one-sided t-test to test the null hypothesis of inferiority versus the alternative hypothesis of non-inferiority (as defined above), 11 sites per treatment group (corresponding to 275 subjects per treatment group or 550 total) will provide an estimated 89% power to conclude non-inferiority. Even if the ICC is higher (0.02), there will still be 83% power to detect non-inferiority.

A second primary outcome is arrest rate. Previous data show a high arrest rate (of around 90%) for ART + FV. We expect a similar arrest rate for SDF. For the power calculation we suppose the unit of analysis to be the person, and consider the binary outcome of 'arrest' defined as all lesions for an individual being arrested. We assume equal (person-level) arrest rates of 90% for the ART+FV and SDF groups, and consider non-inferiority to be within a margin (difference in arrest proportions for ART+FV versus SDF) of 0.09. With the same assumptions as before using a 0.025 alpha level one-sided z test, the targeted sample size of 275 subjects in 11 sites per treatment group will provide an estimated 85% power to conclude non-inferiority. For a higher ICC of 0.02, there will still about 80% power to detect non-inferiority.

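### The 90% person-level arrest rate behind the 85% power is not supported by the source as the protocol describes it, so the stated power is probably, though not certainly, too high

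*Combined protocol and SAP*

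**What the plan says.** Section 11.2 makes arrest a second primary outcome with its own power statement. It says that earlier data (references 2 and 65) "show a high arrest rate (of around 90%) for ART + FV". For the other arm it adds "We expect a similar arrest rate for SDF", citing reference 34 and giving no figure. It takes the person as the unit, and the plan is to "consider the binary outcome of 'arrest' defined as all lesions for an individual being arrested". The input is then "We assume equal (person-level) arrest rates of 90% for the ART+FV and SDF groups". With a margin of 0.09, 275 people in 11 sites per arm, and "using a 0.025 alpha level one-sided z test", it states 85% power at ICC 0.01 and about 80% at ICC 0.02.

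Section 2.1 describes reference 2 as a randomized trial in older adults with root caries that "treated the decayed tooth surfaces with either ART or conventional treatment (using a dental drill"). It "found that ART had a similar restoration survival rate (87% vs. 91"; the figures are percentages, ART first. Fluoride varnish is not mentioned there.

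On lesions per person, section 5.1 requires at least one qualifying lesion. Section 7.1 (Baseline Dental Exam) directs treatment "to all untreated active root or coronal carious lesion with ICDAS-II lesion severity code of 3 or greater". Section 11.4 plans count models for the number of arrested lesions, so it expects people with more than one. No mean or distribution of lesions per person is given.

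**The concern.** The protocol describes one source in two ways: as an arrest rate in section 11.2 and as restoration survival in section 2.1. A surviving filling and an arrested lesion are different events. Section 2.1 also speaks of tooth surfaces and restorations and does not present the 87% as a share of people.

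The unit matters separately. If each lesion has the same chance of arrest, the chance that all of a person's lesions are arrested is at most that per-lesion chance. The two are equal only if everyone has one lesion or a person's lesions succeed or fail together. Section 11.2 moves to the all-lesions responder without this step.

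The responder rate sets the binomial variance, so power against a fixed 0.09 margin falls quickly as the rate drops below 0.90. If the true rate is lower, a trial in which SDF really is non-inferior could end inconclusive on arrest, while readers believe that it had 85% power to settle the question.

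**Working it through.** **Inputs from section 11.2:** 275 per arm, 25 per site, ICC 0.01 (or 0.02), 15% dropout, margin 0.09, one-sided alpha 0.025, equal rates *p* in both arms.

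**Step 1: effective sample size per arm.** After dropout, 275 × 0.85 = 233.75 per arm and 25 × 0.85 = 21.25 per site.
- ICC 0.01: design effect 1 + (21.25 − 1) × 0.01 = 1.2025; effective n = 233.75 / 1.2025 = 194.4.
- ICC 0.02: design effect 1 + 20.25 × 0.02 = 1.405; effective n = 166.4.

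**Step 2: reproduce the plan's power.** Power = Φ(0.09 / √(2p(1−p)/n) − 1.96).
- *p* = 0.90, ICC 0.01: SE = √(0.18/194.4) = 0.0304; Φ(2.958 − 1.960) = 84.1%, stated 85%.
- *p* = 0.90, ICC 0.02: 78.1%, stated about 80%.

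The same effective sample sizes give 88.4% and 83.1% for the pain outcome (stated 89% and 83%), which supports this reading. The program used for arrest is not named. With a constrained-null (Farrington–Manning) variance, the ICC 0.01 results are 81% at 0.90, 73% at 0.87 and 61% at 0.81, so the pattern does not depend on the variance form.

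**Step 3: person-level rates to try.** 0.87 is the section 2.1 figure used directly. The rest are illustrations. Lesion counts and within-mouth correlation are my assumptions, because the documents give neither.
- Two lesions at 90% each, independent: 0.90² = 0.81.
- Two lesions, within-mouth correlation 0.3: 0.81 + 0.3 × 0.90 × 0.10 = 0.837, or 0.84.
- Three lesions, independent: 0.90³ = 0.729, or 0.73.
- Three lesions, correlation 0.3 (beta-binomial): 0.79.
- 0.92: a case more favourable than the plan.

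**Step 4: power with only the rate changed.**

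| Person-level rate | ICC 0.01 | ICC 0.02 |
|---|---|---|
| 0.92 | 90.5% | 85.7% |
| 0.90 (plan) | 84.1% | 78.1% |
| 0.87 | 75.1% | 68.5% |
| 0.84 | 67.7% | 61.0% |
| 0.81 | 61.9% | 55.3% |
| 0.79 | 58.6% | 52.2% |
| 0.73 | 51.5% | 45.6% |

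A mixture also moves the result. If half of the participants have one lesion and half have two independent lesions, at 90% each, the rate is (0.90 + 0.81)/2 = 0.855 and power is 71% at ICC 0.01.

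**Step 5: the enlarged trial.** With 40 more participants (590 in total), the same method at ICC 0.01 gives:

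| Person-level rate | 26 sites | 33 sites |
|---|---|---|
| 0.90 | 87% | 88% |
| 0.87 | 79% | 80% |
| 0.84 | 71% | 73% |
| 0.81 | 66% | 67% |
| 0.73 | 55% | 57% |

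Both site counts are shown because sections 4.2 and 5.4.1 add 4 facilities, while the Protocol Summary and Table 1 add 11.

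**The case against.** A reader might infer that the 85% is a miscalculation. It is not: it follows from its stated inputs to within a point. Section 11.2 also labels the person-level rate openly as an assumption.

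A reader might also infer that the 90% rests on the 87% alone. The documents do not show that. Reference 65 is cited alongside reference 2, and the SDF rate is tied to reference 34, whose title concerns arresting root caries. Neither can be checked here, and 87% is loosely around 90%. What remains is that the only source whose result the protocol reports does not show the event or the unit that section 11.2 needs.

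The strongest objection concerns direction. A lost filling can leave an arrested lesion, so survival may understate arrest. Arm 2 adds biannual varnish, and Arm 1 has a second SDF application at 26 weeks. The lesion-to-person step lowers or preserves the rate only if the per-lesion rate does not vary with lesion count. If failures concentrate in people with many lesions, a pooled per-lesion rate can even fall below the person-level one. These points stand, and they rule out calling the power overstated as a fact.

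It is also fair that the confidence interval compared with −0.09 will show the achieved precision whatever power was stated, and that a lesion-count analysis is already planned. Neither supplies a basis for the power stated for the all-lesions responder. The 40 added participants recover a few points of power but do not settle the input.

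**Conclusion.** The concern holds as one of an unsupported planning input. On what the documents show, 90% is not established as the share of people with all lesions arrested. The stated 85% (about 80% at ICC 0.02) is therefore probably, not certainly, too high. At the planned 275 per arm and ICC 0.01, the protocol's own 87% gives 75%. Two lesions per person give about 68% with correlation 0.3 and 62% if independent; three independent lesions give 52%. All three assume 90% per lesion and lesion counts that the protocol does not report. If everyone had one lesion there would be no loss from the change of unit, and a true rate of 0.92 would give about 90%.

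The point is worth correcting because arrest is a primary outcome with its own non-inferiority decision. It does not affect the validity of the planned test.

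**What to change.** In section 11.2:
- Describe the reference 2 figure as restoration survival, consistent with section 2.1, and say what references 65 and 34 contribute: event, unit and rate.
- State a per-lesion arrest rate and derive the person-level all-arrested rate from it. Use the lesion counts already charted at baseline, blinded and pooled over arms, with a stated range for within-mouth correlation.
- Replace the single 85% / 80% with power over a range that includes 0.90, 0.87 and lower values, at both ICCs, for the current sample size and number of sites. The site count must first be reconciled between sections 4.2 and 5.4.1 and the Protocol Summary and Table 1.

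Keep the endpoint, the 0.09 margin and the analysis unchanged. The cost is a short recalculation and some wording, with no change to conduct. The stated power will probably look less favourable.

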## 5 STUDY ENROLLMENT AND WITHDRAWAL

The *original* 22 housing facilities have a total of 3749 tenants 62 years and older, therefore, we will approach 1368 participants, out of whom 958 will be screened for cavities to obtain the target sample of 550 older adults (approx. 25/housing facility) who have at least one natural tooth. Only individuals with severe medical, cognitive or motor impairments will be excluded. Individuals living independently (our study population) will likely not have severe impairments. Severe medical and motor impairments preventing enrollment will be those which would prevent the individual from completing the dental screening. Severe cognitive impairment will be determined through the consent process. If an individual is unable to explain back to the person obtaining consent what the study involves and what they will do, they will not be consented. Recruitment efforts for the main trial will take place over a two-year period. The study staff will approach tenants at various venues and inquire if they are completely edentulous to check study inclusion/exclusion criteria. Following are the estimates based on our prior study: 73% had at least one tooth; 70% providing consent; 58% with untreated caries. We expect a target of 550 participants to be randomized to the two arms.

The recruitment for all housing sites will follow a 2-stage process: (1) all participants consented will participate in the dental screening; (2) participants found to have non-urgent cavities at the screening and who fulfill the inclusion criteria will be enrolled into the clinical trial.

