## 11.4 Final Analysis Plan (IR-1, RC-4)

Each primary outcome will be compared between the SDF and ART+FV groups. For tooth pain, a 95% confidence interval (CI) based on a t-test for the difference in mean responses (SDF minus ART+FV) will be computed. If this confidence interval lies within the interval  $(-\infty, 8)$  we may conclude 'non-inferiority' of SDF relative to ART+FV treatment. The confidence interval may secondarily be examined to assess possible superiority of one intervention over the other. For arrest rate, a 95% CI for the difference in rates (based on a z statistic) will be computed. If this confidence interval lies within the interval  $(-0.09, 1)$  we may conclude 'non-inferiority' of the SDF relative to ART+FV treatment. As above, possible superiority of one intervention over the other may also be assessed. For other outcomes, we will also compute 95% CI for differences in means (or proportions for binary outcomes). These secondary outcomes will be assessed in an exploratory manner for possibly superiority or inferiority based on appropriate margins.

We will seek to corroborate initial results using a generalized estimating equations (GEE) approach. For each outcome we will fit a GEE (marginal) model that includes a treatment indicator and prognostic variables (including sociodemographic variables, medical conditions, and oral health behaviors). Appropriate link functions (e.g., logit link for binary outcomes and identity link for continuous outcomes) will be specified and an exchangeable working correlation matrix used to allow for correlations within site. The arrest outcome will be analyzed as a binary outcome (as described in the sample size section), and secondarily as the number of arrested lesions assuming an appropriate distribution (e.g., negative binomial) and link function (e.g., log link). Robust t tests with correction for a small number of clusters will be used to test for treatment effects and corresponding 95% confidence intervals computed.

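### The power in 11.2 assumes equal-sized sites and large-sample critical values, and still describes 22 sites and 550 people; restate it for the enlarged design with cluster-level degrees of freedom and a stated spread of site sizes

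*Combined protocol and SAP*

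**What the plan says.** Section 11.2 sizes the trial on 11 sites and 275 people per arm, an ICC of 0.01 (0.02 as the less favourable case) and 15% dropout. For cluster size it says "we assumed an average of 25 subjects recruited per site". Section 5 repeats the figure: 1368 tenants will be approached "to obtain the target sample of 550 older adults (approx. 25/housing facility").

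For pain: "We assume a mean difference of 0 between SDF and ART+FV", a "margin (mean difference) of 8 between SDF and ART+FV arms", an SD of 25, and "The use of a 0.025 alpha-level one-sided t-test". Stated power is 89% at ICC 0.01 and 83% at ICC 0.02.

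For arrest: 90% of people in each arm, a margin of 0.09, "using a 0.025 alpha level one-sided z test". At ICC 0.01, "the targeted sample size of 275 subjects in 11 sites per treatment group will provide an estimated 85% power to conclude non-inferiority"; at ICC 0.02, about 80%.

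No variation in cluster size and no cluster-level degrees of freedom (df) are given. Section 11.4 then specifies "Robust t tests with correction for a small number of clusters" for the GEE treatment comparison, again without stating df.

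Section 11.2 was not revised when the design grew. The Protocol Summary and 4.2 add 40 people. Sections 4.2 and 5.4.1 bring the sites to 26; the Protocol Summary and Table 1 in 4.1 bring them to 33.

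**The concern.** Treatment is assigned to sites, so the precision of the comparison depends on how many sites there are and how evenly they recruit. A t reference on about 20 df has a critical value of 2.086 rather than 1.960. Unequal sites raise the design effect above the equal-size value. Ignoring either makes power look better than it is.

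Table 1 lists original sites of 40 to 498 tenants, so equal recruitment of 25 per site is not realistic. Two non-inferiority conclusions will be read against these power figures, and a reader cannot tell from 11.2 which design they belong to.

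**Working it through.** **1. Reproducing the stated figures.** Inputs are from 11.2. Retained per arm: n = 275 × 0.85 = 233.75. Retained per site: m = 25 × 0.85 = 21.25. Equal-size design effect DE = 1 + (m − 1) × ICC = 1.2025 (ICC 0.01) or 1.405 (ICC 0.02). Effective n per arm = 194.4 or 166.4.

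- Pain: margin/SE = 8 / √(2 × 625 × DE / n) = 3.155 or 2.919.
- Arrest: margin/SE = 0.09 / √(2 × 0.9 × 0.1 × DE / n) = 2.958 or 2.736.
- Power = Φ(margin/SE − 1.960): pain 88.4%/83.1%, arrest 84.1%/78.1%.

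These are within 2 points of 89/83 and 85/about 80.

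**2. Cluster-level df only, sites equal.** Same margin/SE values as noncentrality parameters, noncentral t on 22 − 2 = 20 df: pain 85.1%/79.3%, arrest 80.3%/74.0%. That is 3.3 to 4.1 points below step 1, and 3.9, 3.7, 4.7 and 6.0 points below the stated figures.

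**3. How unequal must the sites be?** Section 5 gives 73% dentate, 70% consenting and 58% with untreated caries: 0.73 × 0.70 × 0.58 = 29.6% of tenants. The six smallest sites (40, 40, 40, 50, 60 and 74 tenants) can then supply about 12, 12, 12, 15, 18 and 22 people, even if every tenant is approached. None reaches 25.

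- Most even recruitment possible: those six supply 90.1 in all, the 91-tenant site supplies 27.0, and the other 15 share (550 − 117.1)/15 = 28.9 each. The CV is about 0.26.
- Recruitment proportional to tenants: the CV of the 22 tenant counts (sum 3749) is 0.68.

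**4. Both adjustments, 22 sites, 550 people.** DE = 1 + ((1 + CV²) × m − 1) × ICC, 20 df.

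| CV | DE (ICC 0.01/0.02) | Pain | Arrest |
|---|---|---|---|
| 0 | 1.203/1.405 | 85.1%/79.3% | 80.3%/74.0% |
| 0.26 | 1.217/1.434 | 84.7%/78.5% | 79.9%/73.1% |
| 0.68 | 1.301/1.602 | 82.3%/73.9% | 77.2%/68.4% |

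A simulated weighted site-level t test (8,000 runs per case) with proportional recruitment gave pain 82%/75% and arrest 78%/70%.

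**5. Enlarged design, 590 people, 15% dropout, both adjustments, df = sites − 2.** Each range runs from CV 0.26 to CV 0.68.

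| Sites | Pain, ICC 0.01 | Pain, ICC 0.02 | Arrest, ICC 0.01 | Arrest, ICC 0.02 |
|---|---|---|---|---|
| 26 | 88–86% | 83–79% | 84–82% | 78–74% |
| 33 | 90–88% | 86–83% | 86–84% | 81–78% |

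The added 40 people offset about 40 who missed the 26-week visit, so the effective gain may be smaller. At 33 sites with 550 people and ICC 0.01, pain is 88.0–86.5% and arrest 83.7–81.9%.

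**The case against.** The stated figures follow from the section's own inputs, so a reader who infers a calculation error goes too far. This is a mismatch of assumptions.

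The 20 df is not in the plan. Section 11.4 first describes plain t and z intervals and brings in the robust t test to corroborate them, although its missing-data paragraph calls GEE the primary analysis. This stands as a caveat. It does not rescue the stated power: the plain intervals show no cluster term, whereas 11.2 relies on a clustering correction.

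Step 1 also does not prove how the figures were obtained. Without dropout (n = 275, m = 25, DE 1.24/1.48), equal sites and 20 df give pain 89.3%/83.5% and arrest 85.2%/78.5%, which match as well. For arrest, a Farrington-Manning calculation without dropout (86.2%/79.5%) is also close, and the specialized program used is not described. But 11.2 says that 15% dropout was assumed for pain and carries the same assumptions to arrest. With dropout and 20 df together, the stated values are not reached.

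The CV of 0.68 describes residents, not recruits. Proportional recruitment would mean about 73 people at the largest site and 6 at the smallest, against a plan of about 25 each. A reader might infer from the worst case that arrest power at ICC 0.02 is below 70%. That needs CV 0.68 and equal weight per person; with the exchangeable weighting planned in 11.4, which down-weights large sites, it is about 70% (pain about 76%).

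Finally, 22 sites and 550 people is a superseded design. This is the strongest objection, and it limits the consequence: at 33 sites the shortfall largely disappears.

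**Conclusion.** The point holds as a mismatch between the power statement and the design and analysis around it. The firm part is the df effect: with 22 sites, 15% dropout and 20 df, power is 4 to 6 points below every stated figure even with equal sites. The unequal-size effect is real but of uncertain size. Beyond the df effect it costs 0.4 to about 3 points at ICC 0.01 and about 1 to 6 points at ICC 0.02, over CV 0.26 to 0.68.

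A reader might infer that the trial as now designed is underpowered. The documents do not support that as a general statement. At 590 people in 33 sites, every figure is above or within about 2 points of the stated one (lowest: arrest 77.8% against about 80%, at ICC 0.02 and CV 0.68). At 26 sites the gap can still reach about 6 points. Which applies depends on a site count that the protocol states in two ways. All of this rests on sites minus 2 as the df, on the section's own ICCs, and on 15% dropout applying to both outcomes.

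**What to change.** 1. Reconcile the number of sites: 26 in 4.2 and 5.4.1, 33 in the Protocol Summary and Table 1.
2. Restate the power in 11.2 for the number of people and sites in force, with DE = 1 + ((1 + CV²)m − 1) × ICC and a t reference on sites minus 2 df. State the CV of recruited (not resident) site size, or show a range such as 0.26 to 0.68. Say whether the 40 added participants are counted as a gain or as replacing lost information, and confirm that dropout is applied to both outcomes.
3. Remove the 22-site figures, or keep them only as the historical calculation with its assumptions named. The CV 0.68 values should not be written in as fact.

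The cost is protocol and SAP wording, with no extra participants. The downside is a less favourable stated power for the 22-site design.
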